2.4.2. Potential Risks

The initial clinical program for vibegron in the treatment of OAB included subjects of both sexes. The Phase 3 program in OAB (RVT-901-3003 and RVT-901-3004) included approximately 15% males, contributing safety data comprising 217 men in addition to those enrolled in Study URO-901-3005. More detailed information about the known and expected benefits and risks from the study and reasonably expected AEs of vibegron may be found in the Investigator's Brochure.

Based on aggregate preclinical, clinical pharmacology, and Phase 2 and 3 studies, AEs of special interest (AESIs) were predefined for specific evaluations in vibegron clinical studies as follows:

- Potential major cardiovascular events
- Hypertension
- AEs suggestive of orthostatic hypotension
- AEs suggestive of cystitis or urinary tract infection
- Elevated aspartate transaminase (AST) or alanine transaminase (ALT) laboratory value requiring that the study drug be temporarily withheld or permanently discontinued
- Neoplasm

In addition, the risk for increases in post void residual urine volume and urinary volume will be closely monitored for post-void retention during the study. The study's enrollment criteria will exclude men with PVR volume ≥ 100 mL at screening and at baseline and those with maximum urinary flow (Qmax) less than 5 mL/second. Post-void residual urine volume will be assessed throughout the study, and subjects with a single PVR volume of ≥ 300 mL or an AE of urinary retention will be withdrawn.

Prespecified definitions of urinary retention and other AESIs are provided in the Adverse Event of Special Interest section ([Section 8.4.6](#)).

3. Objectives and Endpoints

Objectives	Endpoints
Primary Efficacy 
 To assess the efficacy of vibegron compared with placebo in men with OAB symptoms on pharmacological therapy for BPH as defined by micturition and urgency episodes 	Primary Efficacy 
 CFB at Week 12 in the average number of micturition episodes per day CFB at Week 12 in the average number of urgency episodes (urgency: need to urinate immediately) per day

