4.1. Overall Design

This is a Phase 3, randomized, double-blind, placebo-controlled, 2-part, parallel-group, multicenter study to evaluate the safety, tolerability, and efficacy of vibegron 75 mg in men with symptoms of OAB on stable doses of pharmacological therapy for BPH. At Baseline, subjects who meet all eligibility criteria are randomized 1:1 to receive either vibegron 75 mg, or placebo in a double-blind fashion. Randomization will be stratified based on baseline average number of micturition episodes per day (≤ 12 vs > 12), alpha blocker use with or without 5-ARI (yes or no), and urinary incontinence (yes or no).

The study consists of two parts: Part 1 (approximately 80 subjects) and Part 2 (approximately 1008 subjects). Part 2 will proceed following review of 4-week safety data (including orthostatic blood pressure results) of all 80 subjects from Part 1 by an independent DSMB. The independent DSMB will review the safety data throughout the entire study. The 2 study parts are of the same overall design as outlined below but with the following exceptions:

- Part 1 includes additional orthostatic blood pressure and heart rate measurements at Screening, Run-in, Baseline, Week 2, and Week 4 to assess for potential orthostatic changes (pre-dose through 6 hours post dose, except pre-dose for Screening and Run-In).
- Part 2 will include a urodynamics sub-study (approximately 60 subjects), which is described in detail in [Section 8.3.7](#).
 - The rate of enrollment into both the main study and the urodynamics sub-study will be closely monitored. In the case of a discrepancy between the estimated date of completion of enrollment in the urodynamics sub-study and the main study, a decision may be made to continue enrolling only those subjects who are willing to participate in the urodynamics sub-study.

Both study parts will consist of a Screening Period (approximately 1 to 4 weeks), a single-blind therapy plus placebo Run-in Period (approximately 2 weeks), and a randomized double-blind Treatment Period (24 weeks).

Study visit schedules: Visit 1 (Screening), Visit 2 (Run-in), Visit 3 (Baseline), Visit 4 (Week 1), Visit 5 (Week 2), Visit 6 (Week 4), Visit 7 (Week 8), Visit 8 (Week 12), Visit 9 (Week 16), Visit 10 (Week 20), and Visit 11 (Week 24) (End of the Treatment). For subjects enrolled in Part 2 after implementation of Protocol Amendment #2, Visit 4 (Week 1) and Visit 9 (Week 16) will be conducted remotely (via telephone or video call).

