Subjects who complete the Week 24 Visit may be offered the opportunity to enroll in a 28-week extension study URO-901-3006, which will be conducted under a separate study protocol.

Subjects who do not enroll into the extension study will have a Safety Follow-up telephone call

approximately 5 days (\pm up to 2 days) after the subject's last dose of study treatment (ie, or approximately 5 days [\pm up to 2 days] after withdrawal for subjects who discontinue the study early). Additionally, Unscheduled Visit(s) may be arranged as needed.

Approximately 1088 subjects (544 per treatment group: 80 total in Part 1 and 1008 total in Part 2) will be randomized at up to approximately 135 sites in North America (United States and Canada) and Europe to have 924 subjects complete the study (assuming a 15% dropout rate). The sample size justification is provided in [Section 9.2](#).

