8.3.2. Orthostatic Blood Pressure (Part 1 Only)

In addition to routine vital signs (including standard blood pressure assessments), subjects in Part 1 of the study (ie, the first 80 subjects enrolled) will undergo serial blood pressure and heart rate (by pulse) assessments at Screening, Run-In, Baseline, and Weeks 2 and 4. Blood pressure should be assessed as described in [Section 8.3.1](#), with the following additional requirements:

- Triplicate measurements should be obtained for both sitting and standing blood pressure assessments at Hour 0 (pre-dose) and Hours 1, 2, 4, and 6 post dose. (For Screening Visit and Run-In assessments, use Hour 0 as the time from which subsequent assessments are collected.) A singular pulse rate also should be obtained in sitting and standing positions at the same hourly timepoint. Post-dose assessments of blood pressure and pulse may be \pm 15 minutes of each scheduled timepoint.
- Sitting blood pressure and pulse will be measured after the subject has been resting in a sitting position for 5 minutes; standing blood pressure will be measured within 3 minutes of standing (after rising from the sitting position).
- Subjects will be permitted to eat or drink during the 6-hour testing window, however caffeinated beverages will not be allowed.
- Subjects are encouraged to eat breakfast and have the test done at least 1 hour after the meal.
- Subjects should remain relatively inactive and should remain within or close to the facility during the 6-hour test window.
- As stated above in [Section 8.3.1](#), blood draws should be obtained either after all blood pressure assessments are completed or between the 4-hour and 6-hour post-dose blood pressure assessments, provided that blood draws are complete at least 45 minutes before the 6-hour timepoint.

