 - For subjects with systolic blood pressure \geq 140 mmHg **OR** diastolic blood pressure \geq 90 mmHg at **baseline** (Visit 3):
An increase, compared to baseline (Visit 3) at **2 consecutive visits**, in the average of 3 systolic blood pressures by \geq 20 mmHg **or** 3 diastolic blood pressures by \geq 10 mmHg
 - Initiation or increase in dose of medication for treatment of hypertension in any subject

Note 1: The onset date for an AESI hypertension is the first of the dates when the event meets any of the above criteria.

Note 2: An *AE of “increased blood pressure”* should be recorded if, in the investigator’s opinion, an elevated blood pressure measurement is clinically significant but does not fulfill the above definition for hypertension.

- Adverse events consistent with **orthostatic hypotension** as confirmed by orthostatic vital signs
- **Elevated serum aspartate aminotransferase (AST) or alanine aminotransferase (ALT)** lab value requiring that study drug be temporarily withheld or permanently discontinued (see [Sections 8.4.6.1](#) and [8.4.6.2](#)). To date, no concern regarding drug-induced liver toxicity has been identified; however, the Sponsor is monitoring laboratory data for a potential safety signal, consistent with Food and Drug Administration guidance [[FDA Guidance, 2009](#)].
- **Neoplasms**

Serious AESIs and elevated liver enzymes or bilirubin requiring withholding of study drug (see [Section 8.4.6.1](#)) must be reported within 24 hours of the study site personnel's knowledge of the event by marking the appropriate box on the AE eCRF and assigning the most appropriate category. Additional information should be provided as directed in the eCRF Completion Guidelines. AESIs that also meet the definition of an SAE must be reported as an SAE, as described in [Section 8.4.4](#). Nonserious AESIs should be reported within 72 hours of the site personnel's knowledge, using the AE eCRF.

8.4.6.1. Criteria for Temporary Withholding of Study Treatment in Association with Liver Test Abnormalities

Elevated liver enzymes or bilirubin sufficient to require withholding study medication must be reported **within 24 hours of the study site personnel's knowledge of the event** using AESI specific eCRFs/forms/worksheets provided for the study.

Hepatic enzymes will be monitored in accordance with FDA drug-induced liver injury guidelines [[FDA, 2009](#)].

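### Orthostatic hypotension is an AESI only when confirmed by orthostatic vital signs, which are not scheduled for 92.6% of the men, and the SAP's AESI list omits the category

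*Protocol*

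**What the plan says.** **The AESI.** Protocol 8.4.6 lists adverse events consistent with orthostatic hypotension, with the condition "as confirmed by orthostatic vital signs". It gives no numerical criterion and does not say how to classify a suggestive event for which no standing reading exists. Protocol 2.4.2 names the same category more loosely, as "AEs suggestive of orthostatic hypotension", and then refers the reader to 8.4.6 for AESI definitions.

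**The measurements.** Under Protocol 8.3.2, "subjects in Part 1 of the study (ie, the first 80 subjects enrolled) will undergo serial blood pressure" and heart rate assessments, both sitting and standing. Protocol 4.1 gives the timing: "Part 1 includes additional orthostatic blood pressure and heart rate measurements at Screening, Run-in, Baseline, Week 2, and Week 4". Routine blood pressure for everyone else is taken seated (8.3.1). The visit supplement (10.7) gives Part 2 men seated pressure only, and gives Part 1 men seated pressure only from Week 8. In Part 2 the Week 1 and Week 16 visits are remote.

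**Reporting and analysis.** Nonserious AESIs go to the sponsor within 72 hours (8.4.1, 8.4.6). Protocol 9.4.3.1 promises numbers and percentages of men with AESIs, as 8.4.6 defines them, by treatment group. SAP 7.1 lists six AESI categories, and orthostatic hypotension is not one of them. SAP Section 9, which records departures from the protocol, does not mention this.

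**The concern.** The definition applies to the whole trial, but the measurement it depends on is scheduled in a small part of it. Take a Part 2 man who reports postural dizziness or near-syncope. Whether he becomes an AESI case depends on someone deciding to take a standing reading, and not only on what happened to him.

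This matters more here than for a minor category. Every man takes an alpha-blocker (inclusion criterion 4), and the start of Part 2 waited on the DSMB's review of 4-week Part 1 data that included orthostatic pressure. At stake are three things: how fully the AESI category is ascertained, the fast reporting of nonserious cases, and a single grouped comparison between arms on a safety question the trial was partly built to answer. The SAP adds a second problem, because on its list even a confirmed case has no AESI row to appear in.

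**Working it through.** **1. The plan's denominator.** Protocol 4.1 gives about 80 men in Part 1, about 1008 in Part 2, and 544 per arm.
- 80 + 1008 = 1088, and 2 × 544 = 1088. The plan's total reproduces.

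**2. Men with no scheduled standing reading.**
- Part 2 share = 1008 / 1088 = 92.6%.
- Part 1 share = 80 / 1088 = 7.4%.
- The part sizes are approximate. If Part 1 is 72 to 88 men (an assumed ±10%) with the total held at 1088, the share without scheduled readings runs from 1016 / 1088 = 93.4% to 1000 / 1088 = 91.9%.

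**3. Treatment time under scheduled orthostatic surveillance.** Assume no dropout and count all of Weeks 0 to 4 as covered in Part 1.
- Covered: 80 × 4 = 320 man-weeks.
- Planned: 1088 × 24 = 26,112 man-weeks.
- 320 / 26,112 = 1.2%. Within Part 1 alone, 4 / 24 = 16.7%.

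The 1.2% describes scheduled surveillance only. It is not the share of reported events that could be confirmed, because a reading can also be taken when symptoms call for it. As a measure of surveillance it is generous: on double-blind drug the serial readings fall on three visit days per man (Baseline, Week 2, Week 4).

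**4. The texts side by side.**

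| Place | Treatment of orthostatic hypotension |
|---|---|
| Protocol 2.4.2 | Listed as suggestive events; defers to 8.4.6 |
| Protocol 8.4.6 | Confirmation by orthostatic vital signs required |
| Protocol 9.4.3.1 | AESIs per 8.4.6 summarised by arm |
| SAP 7.1 | Absent from the AESI list |
| SAP 9 | No change declared |

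**5. Comparison with other AESIs.** Urinary retention, hypertension and liver enzymes rest on measurements scheduled in both parts. Urinary tract infection relies on a conditional test, but Protocol 10.2 states the symptom trigger for it. For infection and hypertension, 8.4.6 also says how to record findings that fall short of the definition. Orthostatic hypotension in Part 2 has no scheduled measurement, no stated trigger and no such note.

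The size of the under-ascertainment cannot be computed. The documents give neither an event rate nor the frequency of ad hoc standing readings.

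**The case against.** The other side has four good arguments.

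- **Confirmation outside Part 1 is possible.** Protocol 8.4.3 obliges the investigator to arrange further measurements when medically indicated, 8.3.3 has organ systems examined where there is a complaint, and 4.1 allows unscheduled visits. This stands, and it rules out the reading that Part 2 men cannot meet the definition. None of these passages names standing blood pressure, though, so confirmation will vary by site.
- **Event-triggered tests are normal here.** Urine culture depends on a dipstick result or symptoms, and INR is done only on request. This is true, but the urine test has an explicit trigger and this one has none.
- **The events stay visible.** All adverse events are collected through 5 days after the last dose, and SAP 7.1 tabulates treatment-emergent events by preferred term and arm for the whole Safety Analysis Set. This stands in full. A serious event is also reported within 24 hours whatever its AESI status.
- **Limiting serial readings to Part 1 is deliberate.** It serves the staged DSMB review, and requiring confirmation favours specificity. Both are fair, and neither choice is challenged here.

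Two stronger inferences are tempting. A reader might see two rival definitions in 2.4.2 and 8.4.6. The former defers to the latter, so this is loose wording, and the stricter text governs. A reader might also expect a near-zero AESI row to be mistaken for absence of harm. On the SAP's current list there would be no such row, and the preferred-term tables would still show the events.

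**Conclusion.** The point holds as a gap in classification and reporting, not as a loss of safety data. For 92.6% of planned men at all times, and for the remaining 7.4% after Week 4, AESI status for orthostatic hypotension depends on an unscheduled reading. Any summary built on 8.4.6 will under-ascertain the category, as will 72-hour reporting of nonserious cases, and related events will be spread over separate preferred terms with no grouped comparison by arm. Under blinding and 1:1 allocation, nothing in the documents suggests that the shortfall would differ between arms. The expected effect is a low and imprecise count, not a distorted contrast.

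Separately, Protocol 2.4.2, 8.4.6 and 9.4.3.1 and SAP 7.1 do not agree and must be reconciled.

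The conclusion assumes the planned part sizes and that no site-level instruction outside these documents asks for standing readings when symptoms occur.

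**What to change.** - Restore orthostatic hypotension to the AESI list in SAP 7.1, so that it matches Protocol 8.4.6 and 9.4.3.1. If the omission was intended, declare and justify it in SAP Section 9.
- Before unblinding, fix a preferred-term list in the SAP, for example orthostatic hypotension, postural dizziness, presyncope and syncope. Tabulate it by arm over the whole Safety Analysis Set.
- Show the subset confirmed by orthostatic vital signs as a separate row, and state how confirmed status is taken from the recorded data.
- Footnote the table: standing readings were scheduled only in Part 1, to Week 4.
- Bring the wording of Protocol 2.4.2 and 8.4.6 into line if the protocol is amended for other reasons. The SAP changes do not depend on it.

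The cost is a short SAP amendment and one table. The grouped count uses adverse event data already collected, and no visit or procedure is added. The downside is that some non-specific dizziness will be counted, which the confirmed row makes visible.

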8.4.7. Pregnancy Management and Reporting to the Sponsor

In the case of a male subject with a pregnant partner, if the patient agrees, the patient's pregnant partner should be notified and requested to sign a Release of Information form, permitting transfer of information regarding the pregnancy and outcome to the sponsor.

The investigator must inform the subject of his right to receive treatment information. If the subject chooses to receive unblinded treatment information, the individual blind should be broken and the treatment assignment provided to the subject. The study team will remain blinded to the subject's treatment assignment.

In the event that a partner of a male study subject becomes pregnant during the study, if the subject agrees, the subject's pregnant partner should be notified of the subject's study participation and be requested to sign a Release of Information form, permitting transfer of information regarding the pregnancy and outcome to the sponsor. If the subject and the subject's partner agree, the investigator should notify the partner's primary care physician and provide details of the subject's participation in the study and treatment (blinded or unblinded, as applicable).

Partner pregnancies are to be reported to the sponsor **within 24 hours of awareness** by the study site personnel, using the pregnancy reporting forms and information for safety event reporting in **Section 10.3**. The expected date of delivery or expected date of the end of the pregnancy, last menstruation, estimated conception date, pregnancy result, neonatal data, etc. should be included in this information, as available.

If the subject and partner agree, the investigator will follow the medical status of the mother, the pregnancy, as well as the outcome of the infant at birth, and will report the outcome to the sponsor.

8.4.8. Medication Errors

Medication error refers to any unintended error in the dosing and/or administration of the study drug as per instructions in the protocol. Medication errors generally fall into 4 categories as follows:

- Wrong study drug
- Wrong dose (including dosing regimen, strength, form, concentration, amount)
- Wrong route of administration
- Wrong subject (ie, not administered to the intended subject)

Medication errors include occurrences of overdose and underdose of the study drug.

Overdose: Unintentional administration of a quantity of the study drug given per administration or per day that is above the maximum recommended dose according to the protocol. This also takes into account cumulative effects due to overdose (see [Section 8.5](#) for treatment and reporting of overdose). For this study, any dose of vibegron or placebo of 3 or more tablets within a 24-hour window is an overdose. There is no known antidote for an overdose.

Underdose: No underdose is defined for this study.

8.5. Treatment of Overdose

In the event of an overdose (3 more tablets of study drug within 24 hours), the investigator or treating physician should:

- Contact Sponsor's designated Medical Monitor immediately
- Closely monitor the subject for any AEs, SAEs, and laboratory abnormalities
- Report all overdose events on the eCRF, whether or not the overdose is associated with an AE. If the overdose resulted in an AE or SAE, please refer to [Section 10.3](#) for reporting requirements.
- Document the quantity of the excess dose as well as the duration of the overdosing in the eCRF

Decisions regarding dose interruptions or modifications will be made by the investigator in consultation with the Sponsor's designated Medical Monitor based on the clinical evaluation of the subject.

8.6. Safety Measures due to COVID-19 Pandemic

To minimize direct, in-person contact between site personnel and subjects, certain study procedures may be performed remotely by telephone contact or video call. All other procedures should be done in-person while the subject is on-site. Specifically, the following procedures may be done remotely:

- Informed consent (where applicable, per approved IRB/IEC process)
- Medical history
- Demography
- Prior medications (including prior OAB and BPH medication review)
- Collection and dispensation of paper PRO questionnaires
- Collection and dispensation of Bladder Diaries
- Review of AEs/SAEs
- Concomitant medications
- Dispensation of study drug during Double-blind Treatment Phase for visits after Baseline (Visit 3)

If a subject cannot attend the Week 12 visit (Visit 8), the site should bring him/her in for an early withdrawal visit (Visit 11) when safe and feasible.

If a subject misses any other single on-site study visit as a result of the COVID-19 pandemic, then the site should collect the completed Bladder Diary (eg, by curbside pickup, mail, or courier) for review and data entry when feasible, and remotely review AEs/SAEs and concomitant medications. Study drug should be dispensed (eg, curbside pickup or shipped via trackable courier or other methods approved by the Sponsor/CRO), and the next visit's bladder diary should be provided. In such cases, the subject will not be considered lost to follow-up or early withdrawal, if he remains in contact with the site and is compliant with study drug administration, completing study procedures as appropriate, and attends subsequent visits.

9. Statistical Considerations

This section contains a brief summary of the statistical analyses for this study; full details will be provided in the Statistical Analysis Plan (SAP).

The randomized allocation schedule will be generated by the Sponsor or designee and implemented by the vendor of the study. Stratification will be performed across the study (not per site). The statistical analysis of the data obtained from this study will be the responsibility of the Sponsor or designee. At the end of the study, the official, final database will be frozen and unblinded after medical/scientific review has been performed, and data have been declared final and complete. The SAP will be approved prior to data being unblinded.

A subject is considered enrolled in the study at randomization.

